21. SIGNATURE OF STUDY SITES, INVESTIGATORS AND SPONSORS

.....23

Protocol Summary

1、 Objective

To evaluate the clinical outcomes of the Minos™ Abdominal Aortic Stent-Graft and Delivery System in the treatment of Abdominal Aortic Aneurysm in a real-world patient population through a post-market observational registry.

2、 Design

The study is designed as a prospective, multi-centre, post-market, real-world observational registry study. Continuous enrollment is to be conducted for all subjects treated with Minos™ Abdominal Aortic Stent-Graft and Delivery System who meet the inclusion criteria and who voluntarily consent to participate in the study. An enrollment duration period of 24 months is expected for this project and initially, 200 subjects (170 in China and at least 30 in Europe) are to be enrolled. Patient follow up – including CT imaging - will be undertaken in accordance with the usual standard of care at participating sites, and is expected to occur at 30 days, 6 months, 12 months and 2-5 years post-procedure.

3、 Endpoints

1. Primary endpoint

- Technical success rate at 12 months

2. Secondary endpoints

- Incidence of major adverse events at 30 days
- Immediate technical success rate
- Incidence of successful aneurysm treatment at 2-5 years
- All-cause mortality up to 5 years post-procedure
- Aortic aneurysm related mortality up to 5 years post-procedure
- Secondary intervention rates up to 5 years post-procedure
- Aneurysm diameter and variation in aneurysm diameter from 30 days to 5 years post-procedure
- Incidence of type I, III endoleaks from 30 days to 5 years post-procedure
- The incidence rate of stent migration, fracture, stenosis, occlusion and distortion from 30 days to 5 years post-procedure

3. Other endpoints: technical success rate of Hercules balloon and incidence of balloon rupture, where applicable.

4、 Population

Eligible patients will be enrolled according to the inclusion criteria and the exclusion criteria from multiple study sites.

Inclusion criteria

To be enrolled, patients must meet all the following criteria:

- Diagnosis of infrarenal abdominal aortic aneurysm
- Plan to treat with Minos™ Abdominal Aortic Stent-Graft and Delivery System;
- Voluntary participation and completion of Informed Consent Form, with willingness to participate in follow-up to 5 years post-procedure.

Exclusion criteria

- Subjects in whom use of the Minos™ Abdominal Aortic Stent-Graft and Delivery System is contraindicated.

Indications:

- Abdominal Aortic Stent-Graft and Delivery System is indicated for the treatment of abdominal aortic aneurysms with a proximal neck length ≥ 15 mm.

Contraindications:

- Severe stenosis or calcification near the aneurysm, leading to difficulty in achieving apposition of vessel wall and stent graft.
- Difficult access due to severe stenosis or tortuosity in the iliac artery or femoral artery
- Subjects with ruptured aneurysm or acute aneurysm
- Subjects with an infectious aneurysm.
- Those who are allergic to contrast agents or unable to tolerate contrast agents due to renal insufficiency.
- Patients with severe coagulation disorder and/or high risk of postoperative hemorrhage.
- Aneurysmal neck angulation greater than 60°
- Patients with blood supply to vital organs originating from the aneurysmal sac.
- Patients with other comorbidities and whose life expectancy does not exceed one year
- Subjects with connective tissue diseases, such as Marfan syndrome
- Minors and pregnant women
- Subjects who are allergic to nitinol
- Subjects who are considered not suitable for treatment with stent graft.

5. Process

1. Case registration: The Internet registration system will be utilized to consecutively register all eligible patients who have been treated with Minos™ Abdominal Aortic Stent-Graft and Delivery System and voluntarily participated in the study.

2. Signing the Informed Consent Form

3. Case screening: Cases are selected according to inclusion and exclusion criteria

4. Case enrollment

5. Collecting the preoperative and intraoperative data

6. Postoperative follow-up: Imaging follow-up to be conducted in accordance with standard of care at participating sites, to include at 30 days, 6 months, 12 months and annually to 5 years after post-procedure. It is expected that all patients will complete this follow up schedule, but participants will not be excluded in the event that follow up is not completed.

7. Data analysis and summary: All relevant data will be collected and analysed from time to time as the study progress.

Flow chart of study:

Project	Visit1	Visit2	Visit3	Visit4	Visit5	Visit6	Visit (7-10)
Time points	Preoperative	Intraoperative	Discharge	30 days after surgery	6 months after surgery	12 months after surgery	2/3/4/5 years after surgery
Window period ³				±7d	±30d	±60d	±90d
Informed consent ¹	X						
Demographics	X						
Inclusion criteria	X						
Baseline / Disease history	X						
Physical examination	X						
Blood test ²	X		X				
CT	X			X ^{4, 5}	X ⁴	X ⁴	X ⁴
Record of operation process		X					
Evaluation of adverse event		X	X	X	X	X	X

Notes:

1. The subjects shall complete the signing of the Informed Consent Form before enrollment into the study. This will ideally be prior to the treatment procedure. The absence of laboratory test and imaging examination shall not be considered as a protocol deviation.
2. Blood examination includes standard of care tests in the study site, likely full blood count and standard liver and kidney function tests.
3. CT images collected outside of the follow-up window after surgery will not be considered as a protocol deviation.
4. CT imaging may not be undertaken at all follow up points if it is not the treating institution's standard of care to do so. In such cases, alternative imaging can be recorded i.e. USS.
5. This study is an observational study. If the patient undergoes a postoperative CT review before discharge for clinical purposes or as part of the treating institution's standard of care, this imaging examination will be accepted as the 30 days follow up CT, and a further CT scan at 30 days need not be undertaken.

Protocol text

1、 Sponsor information

Name of sponsor: Shanghai MicroPort Endovascular MedTech (Group) Co., Ltd.

Address: [name]

Contact information: [name]

Relevant qualification certificates:

Unified social credit code: 913101150512565326

2、 List of Study sites and Investigators

See Schedule 1 for details. If Schedule 1 is modified, then the version number of the protocol shall not be changed.

3、 Purpose and contents of study

3.1 Objectives

To evaluate the clinical outcomes of the Minos™ Abdominal Aortic Stent-Graft and Delivery System in the treatment of Abdominal Aortic Aneurysm in a real-world patient population through a post-market observational registry.

3.2 Project contents

The study is designed as a prospective, multi-centre, post-market, real-world observational registry study. Continuous enrollment is to be conducted for all subjects treated with Minos™ Abdominal Aortic Stent-Graft and Delivery System who meet the inclusion criteria and who voluntarily consent to participate in the study. An enrollment duration period of 24 months is expected for this project and initially, 200 subjects (170 in China and at least 30 in Europe) are to be enrolled. Patient follow up – including CT imaging - will be undertaken in accordance with the usual standard of care at participating sites, and is expected to occur at 30 days, 6 months, 12 months and 2-5 years post-procedure.

1. Primary endpoint

- Technical success rate at 12 months

2. Secondary endpoints

- Incidence of major adverse events at 30 days
- Immediate technical success rate
- Incidence of successful aneurysm treatment at 2-5 years
- All-cause mortality up to 5 years post-procedure
- Aortic aneurysm related mortality up to 5 years post-procedure
- Secondary intervention rates up to 5 years post-procedure
- Aneurysm diameter and variation in aneurysm diameter from 30 days to 5 years post-procedure
- Incidence of type I, III endoleaks from 30 days to 5 years post-procedure
- The incidence rate of stent migration, fracture, stenosis, occlusion and distortion from 30 days to 5 years post-procedure

3. Other endpoints: technical success rate of Hercules balloon and incidence of balloon rupture, where applicable.

In this study, immediate technical success rate, technical success rate at 12 months, secondary intervention rate, aneurysm diameter and variation in aneurysm diameter, and the incidence of type I and III endoleaks are used as efficacy indicators of the Minos™ Abdominal Aortic Stent-Graft and Delivery System. The incidence of 30-day major adverse events, all-cause mortality, aneurysm related mortality, stent migration, stent fracture, stenosis, occlusion and distortion are used as safety indicators of the Minos™ Abdominal Aortic Stent-Graft and Delivery System.

The presence of proximal endoleaks, and amount of vessel wall apposition will be assessed via immediate post-deployment angiography to determine whether balloon dilatation is indicated. The brand type of balloon will be voluntarily selected by investigators. If the Hercules balloon is used, data pertaining to the Hercules balloon shall be recorded. The success rate of Hercules balloon technique and the rate of balloon rupture are used as efficacy and safety indexes for Hercules balloon device. All relevant data will be collected and analysed from time to time as the study progress.

4、 Study background

Abdominal Aortic Aneurysm (AAA) refers to the localized expansion of abdominal aorta exceeding 50% of the diameter of normal abdominal aorta, of which the main complication is rupture and bleeding, and once ruptured, the mortality is about 90%¹. The incidence rate of abdominal aortic aneurysm is growing year by year. Among the Asian population over 50 years old, the incidence rate of abdominal aortic aneurysm is 25.6%/100,000 in males and is 7.6%/100,000 in females; the incidence in men is about 3.5 times that of women². There is no AAA-related epidemiological data in China, but the detection rate of abdominal aortic aneurysm in China is also increasing year by year with the aging of the population, the application of various imaging techniques and the improvement of clinical understanding.

Currently, clinical surgical treatments of subrenal AAAs mainly include traditional open surgery and endovascular abdominal aortic aneurysm repair (EVAR). Traditional open surgery has the disadvantages of massive trauma and many types of complications. It is usually not considered suitable for patients with heart, lung, kidney, brain and other organ lesions. In 1991, Parodi first reported the application of EVAR in the treatment of AAA. Compared with traditional surgery, it can minimize the degree of surgical invasiveness and reduce the surgical risk, so that the frail and ill patients with AAA can access their therapies and achieve better curative effect. It has become the preferred treatment for most patients³⁻⁵.

EVAR has experienced significant and continuous technological changes and product updates within the last 30 years; however, it still presents several challenges, largely in the context of aneurysms with complex anatomy. For example, if the neck angulation is greater than 60 degrees or the landing zone is less than 15mm, the probability of endoleaks and chronic stent displacement is increased; There may also be an increased incidence of limb stent occlusion; vascular access site complications, arterial dissection, thrombosis or distal embolization as a result of iliofemoral tortuosity, stenosis, or aneurysm. Vascular access complications are directly related to the diameter of the graft delivery system. Studies have shown that a smaller diameter of the delivery system leads to a lower incidence of vascular access complications. Barbanti⁶*et al* conducted a comparative study on 14-18F and 19-26 F sheath devices in percutaneous arterial valve replacement procedures and found that the delivery sheath with lower profile is associated with lower vascular complications (1.0% vs 8.8%, $p < 0.001$), the incidence of life-threatening events and major bleeding events was 0.5% vs 5.4% ($p < 0.001$) and 2.5% vs 5.4% ($p = 0.046$), respectively.

Currently, there are only a few products available in the Chinese market, including Endurant, Excluder, and Zenith. The outer sheath of these device's delivery systems generally reaches 20F or 22F, and they are also expensive, which carries a heavy financial burden to patients. In order to benefit more patients in China and address the clinical challenges described above, Shanghai MicroPort Endovascular MedTech (Group) Co., Ltd. has developed the third-generation Minos Abdominal Aortic Stent-Graft and Delivery System based on the first-generation Aegis Bifurcated Abdominal Aortic Stent-Graft and Delivery System and the second-generation Hercules Bifurcated Abdominal Aortic Stent-Graft and Delivery System. The product adopts an ultra-fine delivery system, with an outer sheath diameter up to 14F. This system can help doctors locate the stent in the abdominal aortic aneurysm neck and iliac artery in a controlled, stable, and accurate way..

Pre-clinical testing was completed prior to CE marking and approval for use in the EU and a domestic pre-clinical investigation of the device in human patients was conducted following successful preclinical trials and testing. A total of 137 patients were enrolled, with an average age of 69.5 years. The 12-month clinical success rate was 89% (121 / 136), the rate of 30-day major adverse events was 1.5% (2/136), the 12-month all-cause

mortality was 7.4% (10 / 136), the aneurysm related mortality was 0.7% (1/136), and the safety and effectiveness have been verified. Therefore, the Minos™ Abdominal Aortic Stent-Graft and Delivery System has been authorized with the Registration Certificate for Medical Device of the People's Republic of China in March 2019, Certificate No.: GXZZ 20193130182. And was CE-Marked in September 2019, Certificate No.: M.2019.106.12584. On this basis, this post-market registry has been commenced to observe the medium and long-term clinical outcomes of Minos™ Abdominal Aortic Stent-Graft and Delivery System in the treatment of AAA in a real-world patient population.

References

- [1] 中华医学会外科学分会血管外科学组腹主动脉瘤诊断与治疗指南. 中国实用外科杂志, 2008, 28(11): 916-917.
- [2] YII M K. Epidemiology of abdominal aortic aneurysm in an Asian population. ANZ J Surg, 2003, 73(6): 393-395
- [4] Lederle F A , Freischlag JA , Kyriakides T C , et al. Long-term comparison of endovascular and open repair of abdominal aortic aneurysm. N Engl J Med, 2012, 367 (21): 1988-1997.
- [6] Barbanti M, Binder RK et al. Impact of low-profile sheaths on vascular complications during transfemoral transcatheter aortic valve replacement. EuroIntervention. 2013 Dec; 9(8):929-35.

5、 Product features, structural composition, working principle, mechanism of action and scope of study

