Endoleak: recorded after surgery according to imaging appearances. Adjuvant therapy such as balloon dilatation due to intraoperative endoleak shall not be included in the analysis. Type I endoleaks are leaks at the proximal or distal attachment sites. Type II endoleaks are caused by retrograde flow through collateral vessels into the aneurysm sac. Type III endoleaks are holes, defects, or separations in the stent-graft material. Type IV endoleaks represent porous graft walls. Endoleaks observed in the same subject at different follow-up timepoints without and which have not been treated shall be calculated once.

Stent migration: movement of stent greater than 10 mm.

Stent fracture: fracture of the metal wire of the stent framework.

Stent stenosis and occlusion: stenosis of the internal diameter of the covered section of the stent is a narrowing of $\geq 50\%$ as seen on imaging; stent occlusion refers to 100% stenosis of stent detected on imaging.

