7.1.7 Other endpoints

Technical success - Hercules balloon: successful introduction and withdrawal of balloon dilation catheter, with accurate balloon positioning, expected expansion diameter reached, no balloon rupture or leakage during operation, and no balloon-related vascular injury.

Balloon rupture: refers to the rupture of balloon dilatation catheter during dilation.

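### The Hercules balloon safety index is rupture alone, so balloon-related vessel injury and balloon leakage have no safety rate, and technical success is labelled efficacy although it measures handling and expansion

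*Protocol*

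**What the plan says.** Section 3.2 of the protocol says that proximal endoleak and wall apposition "will be assessed via immediate post-deployment angiography to determine whether balloon dilatation is indicated". If the operator then chooses a Hercules balloon, its data are recorded. The section assigns the roles of the two balloon rates: "The success rate of Hercules balloon technique and the rate of balloon rupture are used as efficacy and safety indexes for Hercules balloon device".

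Section 7.1.7 defines both rates. Technical success requires "successful introduction and withdrawal of balloon dilation catheter, with accurate balloon positioning", and also "expected expansion diameter reached, no balloon rupture or leakage during operation, and no balloon-related vascular injury". The second definition is short: "Balloon rupture: refers to the rupture of balloon dilatation catheter during dilation".

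In the endoleak definition of section 7.1.6, the protocol adds: "Adjuvant therapy such as balloon dilatation due to intraoperative endoleak shall not be included in the analysis".

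**The concern.** Section 3.2 names two rates and two roles in the same order, shortly after it has separated efficacy from safety indicators for the Minos system. The natural reading is that technical success is the efficacy index and rupture is the safety index. Two things follow.

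First, the safety index describes the integrity of the balloon, not harm to the patient. A vessel injured by an intact balloon does not enter it. The injury appears only as a technical failure of unstated kind, mixed with malposition and under-expansion.

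Second, a rate called efficacy carries no information on why the balloon was inflated. A subject whose proximal leak persists after an uneventful inflation counts as a success.

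At stake is how a reader interprets the two published Hercules figures. A rupture rate of zero under the label of safety may be taken to mean that no vessel was harmed, and a high technical success rate under the label of efficacy may be taken to mean that the leaks were sealed. Neither inference would be warranted.

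**Working it through.** The protocol gives no Hercules rate, number of uses, target or power, so there is no stated figure to reproduce. The check is to score each possible event against the definitions in section 7.1.7.

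| Event in one subject | Technical success | Rupture rate |
|---|---|---|
| Balloon ruptures during dilation | failure | counted |
| Balloon leaks without rupturing | failure | not counted |
| Vessel injured, balloon intact | failure | not counted |
| Expected diameter not reached, no harm | failure | not counted |
| Endoleak or poor apposition persists, inflation otherwise uneventful | success | not counted |

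Rows two to four give the same pair of results. The two rates together cannot distinguish a vessel injury from a balloon that merely failed to expand. Row five shows that correction of the finding that prompted dilatation affects neither rate.

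**Size in general terms.** Let *n* be the subjects in whom a Hercules balloon was introduced, *r* those with rupture, *l* those with leakage but no rupture, *v* those with vascular injury but neither rupture nor leakage, and *h* those who fail for handling or expansion only.

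- Safety index as written: *r*/*n*
- Technical success: (*n* − *r* − *l* − *v* − *h*)/*n*
- Safety index counting all three harms: (*r* + *l* + *v*)/*n*
- Difference between the two safety indexes: (*l* + *v*)/*n*

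**Illustration, all counts assumed.** Take *n* = 60, *r* = 0, *l* = 0, *v* = 3, *h* = 0.

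- Safety index as written: 0/60 = 0%
- Technical success: (60 − 3)/60 = 57/60 = 95%
- Safety index counting all three harms: 3/60 = 5%

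Setting *v* = 0 and *h* = 3 gives the same published pair, 0% and 95%, although no vessel was injured.

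**Range.** If all 200 planned subjects had a Hercules balloon, one injury would shift the safety index by 1/200 = 0.5 percentage points and three by 3/200 = 1.5. With 60 uses the shifts are 1/60 = 1.7 and 3/60 = 5. With fewer uses, each injury weighs more.

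**Do other endpoints fill the gap?** For persistent leak, only in part. Immediate technical success of the Minos system (section 7.1.6) has no endoleak criterion. Endoleak incidence is counted from 30 days (section 3.2) and is an indicator for the stent-graft, not the balloon. For injury, section 13.1 requires every adverse event to be recorded, and its list of device-related events includes arterial wall perforation and access-vessel dissection. That list is tied to the investigational device, so it is not certain that a balloon injury would be classified there. Nothing in it gives a rate among Hercules users.

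**The case against.** The strongest reply is that section 3.2 does not say that the two roles apply respectively. Read jointly, the two rates form one set, which already covers rupture, leakage and vascular injury through technical success. This is a possible reading and would remove the claim that injury lies outside the safety indexes. It would not give injury a rate of its own, because the composite still merges it with handling failures.

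A reader might also infer more than the text supports:

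- *That technical success contains no result of the dilatation.* It requires the expected expansion diameter to be reached, which is a direct mechanical result. What it lacks is the result for the endoleak or apposition.
- *That vessel injuries are lost.* They lower technical success and must be recorded as adverse events. They are missing only from the rupture rate and from any separate balloon rate.
- *That the definitions consistently flatter the balloon.* Counting harms as technical failures lowers the figure labelled efficacy, and a rupture counts against the balloon in both rates.
- *That the study could declare the balloon effective or safe on these figures.* Section 8.3 describes a study without comparison or formal hypothesis test, and no threshold for the balloon exists.
- *That a leak-resolution endpoint is required.* The study objective concerns Minos, and the balloon is an accessory chosen by the operator. Section 4 relates endoleak to neck angulation and landing zone, so closure may depend on more than the balloon. A performance endpoint is a defensible choice. The protocol also specifies angiography only for deciding whether to dilate, not afterwards.

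Finally, one could read leakage in section 7.1.7 as endoleak. Technical success would then address the leak. The phrase places the word directly after balloon rupture, and the protocol elsewhere writes endoleak when it means that, so balloon leakage is the more natural sense. The doubt is a reason to state the meaning.

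**Conclusion.** The point holds as a minor one about definition and labelling. On the natural reading of section 3.2, the Hercules safety index is balloon rupture alone. Balloon leakage and balloon-related vascular injury, which section 7.1.7 already requires to be judged, have no safety rate of their own, so the index can be 0% when vessels were injured. Technical success describes handling and expansion and should not be presented as clinical efficacy.

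The understatement equals the proportion of Hercules subjects with leakage or injury but no rupture. Its actual size cannot be known from the protocol; the 5 percentage points above rest wholly on assumed counts. The conclusion rests on two readings: that the two roles map one to one onto the two rates, and that leakage means balloon leakage. If the first fails, the missing separate rate and the efficacy label remain. If the second fails, the criticism of the efficacy label weakens, but the point about vessel injury stands.

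These are 'other' endpoints in a descriptive registry, collected only where the Hercules balloon is used. The conclusions on Minos are not affected.

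**What to change.** In sections 3.2 and 7.1.7:

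1. Define the Hercules safety index as the occurrence of balloon rupture, balloon leakage or balloon-related vascular injury. Report each component separately as well, with the exact binomial interval that section 8.2 already provides for categorical variables.
2. Use as denominator all subjects in whom a Hercules balloon was introduced.
3. Keep the present composite, but call it technical (device) success and remove the efficacy label.
4. State that leakage means leakage of the balloon.

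Reporting whether the endoleak or poor apposition was resolved is optional, and should be confined to subjects in whom an angiogram after dilatation was obtained.

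The cost is rewording of two short paragraphs. Rupture, leakage and vascular injury must already be assessed to decide technical success, although the operation record should hold them as separate items. The optional resolution item would need one or two further fields. The downside is that the reported balloon safety figure becomes slightly less favourable. Nothing changes in how patients are treated.
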